#### 4.2.4 Safety

Safety endpoints include the following:

- Treatment-emergent adverse events (TEAE) and serious adverse events (SAE).
- Clinically significant changes in laboratory values.
- Changes in vital signs.
- Incidence of anti-drug antibodies.

### 4.3 PREDETERMINED COVARIATES AND PROGNOSTIC FACTORS

For the PK analyses, geographic region and weight will be used as covariates in the model for the primary statistical analysis. The following covariates may be used for further exploration in subgroups:

- Negative binding anti-drug antibodies (ADA) during first dose period
- Negative neutralizing ADA during first dose period

For efficacy analyses, unless stated otherwise, the following stratification factors will be included as covariates in the model or be used to examine treatment effect in subgroups:

- Geographic region (North America vs. Eastern Europe vs. Western Europe)

Sponsor: Amgen Inc.

Statistical Analysis Plan

Protocol No: 20130108

10-December-2018/ Version 2.0

---

- Seropositivity (RF-positive and/or CCP-positive vs. RF-negative and CCP-negative)
- Prior biologic use for RA (1 vs >1)

In case the analysis model doesn't converge, the strata with least number of subjects may be combined to address the convergence issues.

In addition, the following covariates may be used for further exploration in subgroups or as covariates:

- Age Group (<65 years vs  $\geq$ 65 years)
- Race (Caucasian vs Non-Caucasian)
- Gender
- Binding ADA status during first dose period (negative vs positive)
- Neutralizing ADA status during first dose period (negative vs positive)
- Oral Corticosteroid use at baseline (Yes vs No)

Additional baseline demographic and disease characteristics in [Section 9.4](#) may also be considered as covariates in the model for assessing DAS28-CRP change from baseline at week 24.

Analyses that are intended to evaluate the treatment effect and include stratification variables as covariates in the model will be based on the eCRF stratification values, regardless of the subject's IXRS stratification values, to provide unbiased estimates of the effects of treatment and stratification variables without loss of efficiency ([Ke et al, 2017](#)).

For subgroup analyses where the subgroup factor is a stratification variable, an analysis similar to the primary statistical analysis (except the inclusion of the subgroup factor) should be done for each subgroup defined by the eCRF values of the subgroup factor.

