12.4 Randomization

Randomization will be performed by an IXRS. The randomization schedule will be prepared by a statistician not involved in the conduct of the study. Randomization will be stratified by geographic region, seropositivity (RF-positive and/or CCP-positive vs. RF-negative and CCP-negative), and number of prior biologic therapies used for RA (1 vs. > 1).

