12.6.4 Pharmacokinetics

The PK similarity will be demonstrated by comparing the 90% confidence interval (CI) for the GMR of test (ABP 798)-to-reference (US-licensed rituximab or EU-authorized rituximab) **and rituximab [US] to rituximab [EU]** for AUC_{inf} **and for C_{max} following the second** infusion of the first dose with the bounds of 0.8 to 1.25, where $\alpha=0.05$. PK parameters will be calculated using non-compartmental methods. Point estimates and CIs for the GMR will be estimated from an analysis of covariance model using the PK Analysis Set.

Other PK endpoints, $AUC_{0-14\ day}$ after first infusion, $AUC_{0-12\ wk}$ after the first and second infusions of the first dose and C_{max} after the first infusion of the first dose, will be analyzed using the same methods as stated above. Additional PK parameters including the time of C_{max} (t_{max}), terminal elimination half-life ($t_{1/2}$), and the terminal elimination rate constant (λ_z) will be summarized descriptively.

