## PRIMARY STATISTICAL ANALYSIS

The PK similarity will be demonstrated by comparing the 90% CI for the GMR of test (ABP 798)-to-reference (US-licensed rituximab or EU-authorized rituximab) and rituximab [US] to rituximab [EU] for  $AUC_{inf}$  and for  $C_{max}$  following the second infusion of the first dose with the bounds of 0.8 to 1.25. Point estimates and CIs for the GMR will be estimated from an analysis of covariance model using the PK parameter analysis set. For  $AUC_{inf}$  and  $C_{max}$  after second infusion of the first dose, the point estimates and 90% CIs for the GMR for will be estimated using an analysis of covariance model adjusted for weight and geographic region. A sample SAS code for PROC MIXED is displayed below:

CCI

The geometric least square means for each treatment will be presented. The ratios of the geometric means for the comparison of the test treatment to the reference treatment will be obtained by exponentiating the difference of the means on the natural log scale. The CIs will be obtained by exponentiating the CI for the difference between the means on the log scale. Plots of the ratio of geometric means and 90% CI will be displayed.

Additionally, the similarity between PK endpoints of rituximab (US) and rituximab (EU) will be evaluated as well. The GMRs and 90% CIs will be generated for other PK endpoints:  $AUC_{0-14\ day}$ ,  $AUC_{0-12\ wk}$ , and  $C_{max}$  after the first infusion of the first dose by using the same methods as stated above.

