## SENSITIVITY ANALYSES

A sensitivity analysis of all PK parameters will be analyzed similarly to the primary statistical analysis using the PP PK parameter analysis set.

In addition, the following sensitivity analyses will be performed on the PK parameter analysis set:

- The point estimates and CIs for the GMR will be estimated using a model similar to the primary statistical analysis model but excluding all covariates.
- The point estimates and CIs for the GMR will be estimated using the primary statistical analysis model for the subgroups of subjects with negative binding ADA status and negative neutralizing ADA status during first dose period.

Sponsor: Amgen Inc.

Statistical Analysis Plan

Protocol No: 20130108

10-December-2018/ Version 2.0

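### The primary PK ANCOVA leaves out two of the three randomization stratification factors without a stated reason; adding them could tighten the 90% CIs slightly at almost no cost

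*SAP*

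**What the plan says.** Protocol 12.4: "Randomization will be stratified by geographic region, seropositivity (RF-positive and/or CCP-positive vs. RF-negative and CCP-negative), and number of prior biologic therapies used for RA". The last factor separates one prior biologic from several. SAP 3.1 and 3.2 repeat the three factors and define region as North America, Eastern Europe and Western Europe.

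The primary PK model is narrower. SAP 4.3 states that "geographic region and weight will be used as covariates in the model for the primary statistical analysis"; it names no other covariate for that model. SAP 9.5.2 matches it: the GMRs for AUCinf and for Cmax after the second infusion are "estimated using an analysis of covariance model adjusted for weight and geographic region". Protocol 12.6.4 names no covariates: "Point estimates and CIs for the GMR will be estimated from an analysis of covariance model using the PK Analysis Set".

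For efficacy, SAP 4.3 says "the following stratification factors will be included as covariates in the model or be used to examine treatment effect in subgroups" and lists all three. The stratification factors are then in the CD19+ depletion model (SAP 9.6.1), the DAS28-CRP models (9.7.1), the ACR models (9.7.2) and the hybrid ACR models (9.7.3).

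The PK sensitivity analyses in SAP 9.5.2 use the per-protocol PK set, the ADA-negative subgroups, or a fit "using a model similar to the primary statistical analysis model but excluding all covariates". None adds seropositivity or prior biologics. SAP 10, which lists changes from the protocol analysis, does not discuss PK covariates.

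**The concern.** A factor that is balanced by design but left out of the model keeps its share of the outcome variance in the residual. If it predicts the outcome, the reported standard error is larger than the true sampling error of the treatment contrast, and the interval is wider than it has to be. The analysis that carries the primary objective is the one that departs from the stratified design, while the secondary and descriptive models follow it.

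At stake is a little precision on the primary 90% CIs and on the rituximab (US) vs rituximab (EU) comparison. That comparison uses the same model and decides whether the reference arms are pooled for efficacy (SAP 9.7).

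**Working it through.** **Inputs from Protocol 12.2:** about 100 subjects per arm, 15% dropout (so 85 per arm), CV 40%, true GMR 1, margin 0.8 to 1.25, significance level 0.05 per comparison, stated power above 90%.

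**Assumed input:** the partial R² of seropositivity and prior biologics together for log exposure, given region and weight. The documents give no value. I use 0 to 5%, with 10% as an extreme.

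**1. Reproduce the stated power.**
- Log-scale SD = √ln(1 + 0.40²) = √ln 1.16 = 0.3853.
- SE = 0.3853 × √(2/85) = 0.0591.
- Power (normal) = 2Φ(ln 1.25/SE − 1.645) − 1 = 2Φ(0.2231/0.0591 − 1.645) − 1 = 96.7%. Integrating over the variance estimate (t-based) gives 96.6%.
- At 100 per arm the normal result is 98.6%.

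The stated figure is met per test. About 65 evaluable subjects per arm would give 90%.

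**2. Degrees of freedom.** The current model has an intercept, two treatment, two region and one weight term, so 3 × 85 − 6 = 249. Two more terms leave 247. The t quantile stays at 1.651.

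**3. Effect of adding both factors.** Half-width on the log scale = t × 0.3853 × √(1 − R²) × √(2/85).

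| Partial R² | Half-width | Ratio to current | Per-test power (t-based) |
|---|---|---|---|
| 0% | 0.0976 | 1.000 | 96.61% |
| 1% | 0.0971 | 0.995 | 96.76% |
| 2% | 0.0966 | 0.990 | 96.92% |
| 5% | 0.0951 | 0.975 | 97.35% |
| 10% | 0.0926 | 0.949 | 97.99% |

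Around a GMR of 1, the current interval is about 0.907 to 1.103. At R² = 5% it becomes 0.909 to 1.100.

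**4. Cost if the factors are irrelevant, and coverage.** This was simulated with 4,000 trials per setting, 85 per arm and stratified permuted blocks. The stratum prevalences were assumed (region 20/60/20%, 80% seropositive, 35% with more than one prior biologic).
- At R² = 0, the mean width ratio was 1.0003, and the fuller model was narrower in 35% of trials.
- Coverage of the nominal 90% CI under the current model was about 90% at R² = 0 and about 92% at R² = 10%. The simulation error is about √(0.9 × 0.1/4000) = 0.5 points.

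**5. Credit for weight and region.** Protocol 12.2 does not say that the 40% CV is adjusted for anything. If weight and region already explain 10% of the variance (assumption), current power is about 98.0%. A further 1 to 5% then gives about 98.1 to 98.5%.

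**The case against.** The strongest reply is that this is a consistent, prespecified choice with no validity problem. SAP 4.3 and 9.5.2 agree, the protocol leaves the covariates open, and SAP 4.3 sets separate lists for PK and efficacy. Dosing is a flat 1000 mg, so weight is a natural PK covariate, whereas nothing in the documents ties seropositivity or prior biologics to exposure. The no-covariate fit already gives some check on covariate choice. Per-test power is near 97% against a stated figure above 90%. All of this stands, and it sets the severity. It does not explain why two factors used in randomization and in the PD model were left out. The no-covariate fit removes terms, so it cannot show what the missing ones would do.

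Three stronger readings are tempting and are not supported.
- A reader might infer that the primary intervals are in fact too wide. That holds only if a factor predicts exposure beyond weight and region, and the documents do not show it.
- A reader might infer that similarity could be wrongly claimed. The omission does not bias the GMR, and any effect on coverage is conservative.
- A reader might infer that adding the factors fully matches the analysis to the design. The PK parameter set is a subset of randomized subjects, analysed by treatment received, and SAP 4.3 takes stratum values from the eCRF rather than the IXRS. The design balance therefore carries over only approximately.

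In the other direction, the primary objective needs both endpoints to pass against both references, so per-test figures understate the possible gain. With an assumed correlation of 0 to 0.8 between the endpoints, the simulated probability that all four tests pass is 87.9 to 90.2% now and 90.4 to 92.1% at R² = 5%. At R² = 1% the gain is about 0.5 points. These gains rest on the same unsupported R².

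**Conclusion.** The omission is real and unexplained, and no planned PK analysis covers it. Its consequence is conditional and small. Over an assumed partial R² of 0 to 5%, adding both factors changes CI width by 0 to −2.5% and moves per-test power at 85 per arm from 96.6% to at most about 97.4%. The power gain is smaller if weight and region already reduce the 40% CV. If the factors are unrelated to exposure, nothing is gained and the loss is negligible. I am confident of the omission but not of any particular benefit. Low severity: a nearly free improvement in precision, not a defect in validity.

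**What to change.** Before unblinding, revise SAP 4.3 and 9.5.2 so that the primary PK ANCOVA includes seropositivity and number of prior biologics (1 vs more than 1) alongside region and weight. Use the same model for all three comparisons: ABP 798 vs rituximab (US), ABP 798 vs rituximab (EU), and rituximab (US) vs rituximab (EU). The timing matters because the last of these decides whether the reference arms are pooled for efficacy. Keep the no-covariate model as the sensitivity analysis. The provision in SAP 4.3 for combining strata is not needed here: it is triggered by non-convergence, which is essentially irrelevant to a linear ANCOVA.

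The cost is two sentences of SAP text, two model terms and two residual degrees of freedom. The data are already collected, and Protocol 12.6.4 names no covariates, so it needs no change.

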## 5. DEFINITIONS

### 5.1 GENERAL

#### **Actual Treatment Received**

The actual treatment received is the investigational product (IP) treatment the subject actually received, regardless of what the subject was randomized to. In cases where a subject received more than 1 IP during a dose, the actual treatment received for that dose will be based on the first IP infusion of the dose the subject received. The actual treatment received for the entire study will be based on the combination of the actual treatment received for the first infusion of the two doses. In cases where a subject received only the 1st dose of IP, the actual treatment received for the entire study will be determined by the actual treatment of the 1st IP dose and the intended treatment of the 2nd

Sponsor: Amgen Inc.

Statistical Analysis Plan

Protocol No: 20130108

10-December-2018/ Version 2.0

---

dose per protocol. The actual treatment for the study will be unplanned if the sequence of the actual treatment of each dose are not described in the protocol.

Specifically, by design for each subject, 2 doses will be administered during the study where each dose consists of 2 infusions, and each infusion consists of 2 boxes. In the cases where a subject receives mismatched boxes (differing IP) among the 2 possible boxes within an infusion, if either box is ABP 798 then the actual treatment for the infusion will be ABP 798.

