### 3.1 SAMPLE SIZE CONSIDERATIONS

Approximately 300 subjects will be randomized in a 1:1:1 ratio to receive ABP 798, rituximab (US), or rituximab (EU), stratified by geographic region (North America, Eastern Europe, and Western Europe), seropositivity (rheumatoid factor (RF)-positive and/or anti-cyclic citrullinated peptide (CCP)-positive vs. RF-negative and CCP-negative), and number of prior biologic therapies used for RA (1 vs. >1). The sample size will provide > 90% power to demonstrate similarity on the primary PK endpoints based on an assumption of between-subject variability (as measured by coefficient of variation) of 40%, true geometric mean ratio (GMR) of 1 among ABP 798, rituximab (US), or rituximab (EU), a margin of (0.8, 1.25) and 15% dropout by week 24. PK similarity will

Sponsor: Amgen Inc.

Statistical Analysis Plan

Protocol No: 20130108

10-December-2018/ Version 2.0

be tested between ABP 798 versus rituximab (US) and ABP 798 versus rituximab (EU), each with a significance level of 0.05. The similarity between rituximab (US) and rituximab (EU) will be evaluated as well.

With the planned sample size, there is 94% probability that the 90% CI of the difference between the ABP 798 arm and the pooled rituximab (rituximab [EU] and rituximab [US]) arm and 83% probability that the 90% CI of the difference between test (ABP 798) and reference (rituximab [EU] or rituximab [US]) in DAS28-CRP change from baseline at week 24 will fall into the equivalence margin of  $\pm 0.6$  (EULAR response criteria), assuming a standard deviation of 1.4 ([Volkmann et al, 2010](#)) and true mean difference of 0.

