## 5.2 PHARMACOKINETIC

Pharmacokinetic parameters will be calculated from serum concentration-time data using noncompartmental analysis (NCA) methods using Phoenix WinNonLin® Version 6.4 or higher (Pharsight Corp, St. Louis, MO). The following PK parameters will be reported for serum rituximab and ABP 798, using actual elapsed sampling times:

Variable	Definition
$C_{max1}$	Maximum observed serum concentration following Dose 1 Infusion 1
$C_{max2}$	Maximum observed serum concentration following Dose 1 Infusion 2
$t_{max1}$	Time to which the maximum serum concentration was observed following Dose 1 Infusion 1
$t_{max2}$	Time to which the maximum serum concentration was observed following Dose 1 Infusion 2
TLST1	Time of last quantifiable concentration following Dose 1 Infusion 1

Sponsor: Amgen Inc.

Protocol No: 20130108

Statistical Analysis Plan

10-December-2018/ Version 2.0

CLST1	Last quantifiable concentration following Dose 1 Infusion 1 over first 14 days postdose (day 15)
AUC 0-14 day	Area under the serum concentration-time curve from time 0 on day 1 prior to the first infusion of the first dose to last quantifiable concentration associated with Dose 1 Infusion 1 over the first 14 days postdose (day 15)
TLST2	Time of last quantifiable concentration associated with Dose 1 Infusion 2
CLST2	Last quantifiable concentration after Dose 1 Infusion 2
AUC 0-12 wk	Area under the serum concentration-time curve from time 0 on day 1 prior to the first infusion of the first dose to last quantifiable concentration over 12-week profile
AUC inf	Area under the serum concentration-time curve from time 0 on day 1 prior to the first infusion of the first dose extrapolated to infinity; calculated as AUC last + CLST2/λ z , where AUC last is the AUC from time 0 to the last quantifiable concentration up to week 12 (i.e. AUC 0-12 wk )
t 1/2	Terminal elimination half-life determined from time 0 to Week 12 profile; calculated as ln(2)/ λ z
λ z	Terminal elimination rate constant
CL	Clearance
AUMC	Area under the first moment curve
MRT	Mean residence time; calculated as AUMC inf /AUC inf – TI /2, where TI represents infusion duration and AUMC inf is the area under the moment curve from the time of first dosing extrapolated to infinity.
AUC 0-12 wk /AUC inf	calculated as AUC 0-12 wk /AUC inf

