## 6.5 PHARMACOKINETIC PARAMETER ANALYSIS SET

The PK parameter analysis set is defined as the subset of subjects in the safety analysis set who received the full protocol-specified dose on Day 1 and had an evaluable ABP 798 or rituximab serum concentration time profile. The PK parameter analysis set will be used for the primary statistical analysis of PK endpoints. Pharmacokinetic parameter data from subjects will be analyzed according to the actual treatment received. Subjects to be excluded from the PK parameter analysis set will be determined based on a blinded data review prior to database lock.

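### A first dose that mixes products is labelled by its first infusion, so Cmax after infusion 2 can be credited to the wrong product in the primary PK test, and no rule sets it aside

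*SAP*

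**What the plan says.** - **Labelling.** SAP 5.1 (Actual Treatment Received) explains that each dose is two infusions and each infusion two boxes. If products are mixed within a dose, "the actual treatment received for that dose will be based on the first IP infusion of the dose the subject received". If the two boxes of one infusion differ, "if either box is ABP 798 then the actual treatment for the infusion will be ABP 798". The rules nest: the box rule names a single infusion, and the dose then takes the name of its first infusion.
- **Use in the primary analysis.** SAP 6.5: "Pharmacokinetic parameter data from subjects will be analyzed according to the actual treatment received". Entry to that set needs the full Day 1 dose and an evaluable profile. Nothing requires a single product throughout the first dose.
- **Endpoints.** SAP 4.1 and 9.5.2 make AUCinf and Cmax2 primary. SAP 5.2 defines Cmax2 as "Maximum observed serum concentration following Dose 1 Infusion 2". AUCinf runs from time 0 on Day 1, so it covers both infusions.
- **Exclusions.** SAP 9.5.2 names an incomplete infusion, a long interruption and an unusually long infusion as reasons for non-evaluability. It does not name a product mix-up. SAP 5.2 drops Cmax2 by rule when the last sample after infusion 1 falls more than 2 days from Day 15. Other exclusions from the sets in 6.5 and 6.6 are settled in blinded review.

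**The concern.** A subject given rituximab on Day 1 and ABP 798 on Day 15 is a rituximab subject under SAP 5.1, yet the Cmax2 was measured after ABP 798. A subject given one ABP 798 box and one rituximab box at infusion 1 is, by default, analysed as ABP 798. A label of this kind is serviceable for safety tables. In a product-to-product ratio it puts one product's exposure into another product's mean.

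The direction is what matters. In a similarity test, blending two arms that truly differ moves the expected ratio between them towards 1, and so towards a claim of similarity. The two sensitivity analyses run on the PK parameter set (without covariates, and in ADA-negative subjects) keep the same labels. The per-protocol PK set helps only if the mix-up is recognised as an important deviation.

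US/EU mixing acts in the same way on the US-to-EU ratio. That comparison decides, in SAP 9.7, whether the reference arms are pooled for DAS28-CRP. The box rule does not say how an infusion of one US and one EU box is labelled.

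**Working it through.** **Inputs from the documents (SAP 3.1 and 9.5.2).** 300 randomized 1:1:1, so 100 per arm; 15% dropout, so 85 per arm; CV 40%; margin 0.80 to 1.25; 90% CI, i.e. two one-sided tests at 0.05; planning GMR 1.

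**Assumptions.** The number m of mixed-product subjects is not given, so a range is shown. The true Cmax2 ratio is set at the margin (1.25; 0.80 is symmetric). Crossed subjects carry the other product's full Cmax2, except in the carry-over rows.

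**Step 1: the plan's own figure.**
- SD of log = √ln(1 + 0.40²) = 0.385
- SE = 0.385 × √(2/85) = 0.0591
- ln 1.25 = 0.2231
- Power at GMR 1 = 2Φ(0.2231/0.0591 − 1.645) − 1 = 96.7% (96.6% by simulation with t)

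The plan states "The sample size will provide > 90% power to demonstrate similarity on the primary PK endpoints". That is reproduced per comparison and endpoint.

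**Step 2: dilution.** If m of the 85 subjects labelled reference carry the other product, that arm's expected log mean moves a fraction m/85 of the way to the other product. The expected log ratio d is then:
- m in one arm: d = 0.2231 × (1 − m/85)
- m in each arm: d = 0.2231 × (1 − 2m/85)

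**Step 3: false-similarity rate.** The pass probability is Φ((0.2231 − d)/SE − 1.645) + Φ((0.2231 + d)/SE − 1.645) − 1. For m = 1 in one arm, 0.2231 − d = 0.0026 and 0.0026/0.0591 = 0.044. This gives Φ(0.044 − 1.645) = Φ(−1.60) = 5.5%; the other two terms cancel (Φ ≈ 1).

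| Mixed subjects m | 0 | 1 | 2 | 3 |
|---|---|---|---|---|
| One arm: expected ratio | 1.250 | 1.247 | 1.244 | 1.240 |
| One arm: false similarity | 5.0% | 5.5% | 6.0% | 6.5% |
| Each arm: false similarity | 5.0% | 6.0% | 7.1% | 8.4% |
| One arm, 70% of the difference expressed | 5.0% | 5.3% | 5.7% | 6.0% |
| Each arm, 70% of the difference expressed | 5.0% | 5.7% | 6.4% | 7.2% |

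The 70% rows are an assumed allowance for carry-over from infusion 1. If the true ratio is 1, then d = 0 for every m and there is no bias.

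**Step 4: cost of excluding the values.** The false-similarity rate returns to 5.0%. Power at GMR 1, per comparison and endpoint, goes from 96.7% to 96.6% (1 excluded from one arm), 96.2% (5) or 95.7% (9). With 9 excluded from each of two arms it is 94.6%.

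**The case against.** **The event is a contingency.** SAP 5.1 says what happens if products are mixed; it does not say that this is expected or occurred. The upper figure, 8.4%, needs six crossed subjects among 170, a true ratio exactly on the margin, and Cmax2 judged alone although AUCinf must pass too. This stands, and it limits the size.

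**A mixed Day 1 may already be out.** Protocol 8.5.1 specifies the dose by product, so one box of each could be read as the full dose of neither and fail entry to the PK set. That reading is possible but nowhere stated, and SAP 5.1 gives such an infusion a label. It does not help when the mismatch is at infusion 2.

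**The review is not wholly without information.** Protocol 8.5.4 has an unblinded pharmacist and some unblinded CRO staff for accountability. SAP 9.2 logs and reviews deviations, and SAP 9.1 and 9.3.1 list actual treatment and lots. So it would be too strong to infer that the mix-up cannot be seen. What remains is that no criterion is written, and a blinded reviewer may know of a kit error without knowing whether the products differed.

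**The direction is not universal.** A reader might infer that any misattribution favours similarity. A US subject given EU product at infusion 2 moves the ABP 798-to-US ratio towards the ABP 798-to-EU ratio, which may lie further from 1. The pull towards 1 is assured, in expectation, only for the ratio between the two products that were mixed, and only if they differ.

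**Conclusion.** The gap is real. Followed as written, SAP 5.1 and 6.5 credit Cmax2 to the wrong product, and mix AUCinf, whenever infusion 2 differs from infusion 1. They also count a mixed ABP 798/rituximab infusion 1 as ABP 798 by default. No stated rule prevents either.

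The size is modest: 5.5% to 6.5% false similarity with one to three such subjects in one arm, and 6.0% to 8.4% with that number in each arm, against 5.0%. These figures rest on 85 per arm, CV 40%, a true ratio at the margin, full expression of the other product's Cmax2, and Cmax2 taken alone. Carry-over lowers them.

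A reader might also infer that any ABP 798 box in the first dose moves the subject to the ABP 798 arm. The text does not say so: a subject with rituximab at infusion 1 stays in the rituximab arm whatever is given at infusion 2.

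The correction is worth making before lock because it concerns a primary endpoint, can favour the sponsor's conclusion, and is cheap.

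**What to change.** Keep the SAP 5.1 rule for safety and ADA. In SAP 5.2, 6.5 and 6.6 add a parameter-level rule in the style of the existing timing exclusions:

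- For a subject who received more than one product within the first dose, every PK parameter that spans or follows the mismatch is listed but excluded from the primary and per-protocol PK analyses.
- Mismatch at infusion 2: exclude Cmax2, AUCinf and AUC0-12 wk, and keep the earlier Cmax1 and AUC0-14 day. Mismatch at infusion 1: exclude all parameters.
- State that the rule also covers US/EU box mismatches.
- Apply it from box and lot records before database lock, by a pre-specified program or by unblinded staff independent of the analysis.
- If any such subject exists, report the result under the 5.1 labels as a sensitivity analysis.

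The cost is a few sentences and a few subjects' values. Power per test stays above 90% (about 96% with 5 excluded from one arm). Dropping whole subjects after unblinding would be blunter: it would discard correctly attributed infusion 1 parameters and depart from the SAP's practice of settling exclusions before lock.
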